**Study Population:**

Inclusion:

1. Must understand, agree and be able to comply with the requirements of the protocol. Subjects must be willing and able to provide voluntary consent to participate and sign a Consent Form prior to study-related activities;
2. Women aged 18 and above
3. Vulvar infection with HPV types 16 and/or 18 confirmed by screening biopsy;
4. Vulvar tissue specimen/blocks must be collected within 10 weeks prior to anticipated date of first dose of study drug and have histologically confirmed vulvar HSIL by the Pathology Adjudication Committee at screening;
5. Must be judged by the Investigator to be an appropriate candidate for the protocol-specified procedure (i.e. excision or biopsy) required at Week 48;
6. Must have vulvar HSIL that is accessible for sampling by biopsy instrument and of adequate size to ensure that a visible lesion remains after an approximately 4 mm screening biopsy;
7. Must have vulvar HSIL that can be completely demarcated for area measurement;
8. Must meet one of the following criteria with respect to their reproductive capacity:
  - a) Is post-menopausal as defined by spontaneous amenorrhea for more than 12 months or spontaneous amenorrhea for 6-12 months with FSH level >40 mIU/mL;
  - b) Is surgically sterile due to absence of ovaries or due to a bilateral tubal ligation/occlusion performed more than 3 months prior to screening;
  - c) Women of Child Bearing Potential (WOCBP) are willing to use a contraceptive method with failure rate of less than 1% per year when used consistently and correctly from screening until 6 months following the last dose of investigational product. Acceptable methods are the following:
    - i) Hormonal contraception: either combined or progestin-alone including oral contraceptives, injectable, implants, vaginal ring, or percutaneous patches. Hormonal contraceptives must not be used in subjects with a history of hypercoagulability (e.g., deep vein thrombosis, pulmonary embolism);
    - ii) Abstinence from penile-vaginal intercourse when this is the subject's preferred and usual lifestyle;
    - iii) Intrauterine device or intrauterine system;
    - iv) Male partner sterilization at least 6 months prior to the female subject's entry into the study, and this male is the sole partner for that subject.
9. Has normal screening electrocardiogram (ECG) or screening ECG with no clinically significant findings as judged by the Investigator.

Exclusion:

- 1) Untreated microinvasive or invasive cancer;
- 2) Biopsy-proven Vaginal Intraepithelial Neoplasia (VAIN) and are not undergoing medical care and/or treatment for VAIN;
- 3) Biopsy-proven Anal Intraepithelial Neoplasia (AIN) and are not undergoing medical care and/or treatment for AIN;
- 4) Biopsy-proven Cervical Intraepithelial Neoplasia (CIN) 2/3 and are not undergoing medical care and/or treatment for CIN;
- 5) Biopsy-proven differentiated VIN;
- 6) Vulvar HSIL that is not accessible for sampling by biopsy instrument;
- 7) Vulvar HSIL that is not of adequate size to ensure that a visible lesion remains after biopsy;
- 8) Treatment for genital warts within 4 weeks prior to screening;
- 9) Any previous treatment for vulvar HSIL (e.g. with surgery and/or imiquimod) within 4 weeks prior to screening;
- 10) Allergy to imiquimod 5% cream or to an inactive ingredient in imiquimod 5% cream;
- 11) Is pregnant, breastfeeding or considering becoming pregnant within 6 months following the last dose of investigational product;
- 12) Presence of any abnormal clinical laboratory values greater than Grade 1 per Common Toxicity Criteria for Adverse Events (CTCAE) v 4.03 within 45 days prior to Day 0 **or** less than Grade 1 but deemed clinically significant by the Investigator;
- 13) Immunosuppression as a result of underlying illness or treatment including:
  - a) History of or positive serologic test for HIV at screening;
  - b) Primary immunodeficiencies;
  - c) Long term use ( $\geq 7$  days) of oral or parenteral glucocorticoids at a dose of  $\geq 20$  mg/day of prednisone equivalent (use of inhaled, nasal, otic, and ophthalmic corticosteroids are allowed);
  - d) Current or anticipated use of disease modifying doses of anti-rheumatic drugs (e.g., azathioprine, cyclophosphamide, cyclosporine, methotrexate) and biologic disease modifying drugs such as TNF- $\alpha$  inhibitors (e.g. infliximab, adalimumab or etanercept);
  - e) History of solid organ or bone marrow transplantation;
  - f) Any prior history of other clinically significant immunosuppressive or clinically diagnosed autoimmune disease that may jeopardize the safety of the subject or require therapy that would interfere with study assessments or endpoint evaluation, or otherwise impact the validity of the study results.
- 14) History of previous therapeutic HPV vaccination (licensed prophylactic HPV vaccines are allowed, e.g. Gardasil®9, Gardasil®, Cervarix®);
- 15) Received any non-study related non-live vaccine within 2 weeks of each study dose;
- 16) Received any non-study related live vaccine (e.g. measles vaccine) within 4 weeks of each study dose;
- 17) Significant acute or chronic medical illness that could be negatively impacted by the electroporation treatment as deemed by the Investigator;
- 18) Current or history of clinically significant, medically unstable disease which, in the judgment of the Investigator, would jeopardize the safety of the subject, interfere with study assessments or endpoint evaluation, or otherwise impact the validity of the study results
  - a) Chronic renal failure, angina, myocardial ischemia or infarction, class 3 or higher congestive heart failure, cardiomyopathy, or clinically significant arrhythmias;
  - b) Treatment for non-anogenital malignancy within 2 years of screening, with the exception of superficial skin cancers that only require local excision;

- c) Bleeding or clotting disorder or use of blood thinners (e.g. anticoagulants or antiplatelet drugs) that would contraindicate IM injections within 2 weeks of Day 0;
  - d) History of seizures unless seizure free for 5 years with the use of one or fewer antiepileptic agents;
  - e) Sustained, manually confirmed, sitting systolic blood pressure >150 mm Hg or <90 mm Hg or a diastolic blood pressure >95 mm Hg at Screening or Day 0;
  - f) Resting heart rate <50 bpm (unless attributable to athletic conditioning) or >100 bpm at Screening or Day 0;
  - g) Prior major surgery within 4 weeks of Day 0;
- 19) Participation in an interventional study with an investigational compound or device within 4 weeks of signing informed consent (participation in an observational study is permitted);
- 20) Less than two acceptable sites available for IM injection considering the deltoid and anterolateral quadriceps muscles;
- a) Tattoos, keloids or hypertrophic scars located within 2 cm of intended treatment site;
  - b) Cardioverter-defibrillator or pacemaker (to prevent a life-threatening arrhythmia) (unless deemed acceptable by a cardiologist);
  - c) Metal implants or implantable medical device within the intended treatment site (i.e. electroporation area);
- 21) Vulnerable populations:
- a) Active drug or alcohol use or dependence that, in the opinion of the Investigator, would interfere with adherence to study requirements;
  - b) Prisoner or subject who is compulsorily detained (involuntarily incarcerated) for treatment of either a psychiatric or physical (i.e. infectious disease) illness;
  - c) Active military service personnel who have the potential to be relocated;
  - d) Study-related staff or family members of study-related staff;
- 22) Any illness or condition that in the opinion of the Investigator may affect the safety of the subject or the evaluation of any study endpoint.

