#### **4.3.2 CRITERIA FOR WITHDRAWAL FROM THE STUDY**

All subjects who begin treatment should be encouraged to complete all phases of the study, including those who discontinue treatment. A subject may voluntarily withdraw from study participation at any time. A subject may be withdrawn at any time at the

discretion of the Investigator for any maternal obstetrical or medical complications after consultation with the medical monitor.

Subjects who become ineligible to continue on study based on no longer meeting exclusion criteria should be discontinued from study treatment, managed per routine standard of care and should continue on study without further biopsy.

Subjects who are withdrawn from study participation after starting treatment will not be replaced. Reasons for study withdrawal will be recorded in the electronic case report form (eCRF) and the subject's source document.

Should a subject fail to attend the clinic for a required study visit, the site should attempt to contact the subject and reschedule the missed visit as soon as possible. The site should also counsel the subject on the importance of maintaining the assigned visit schedule for follow-up and treatment of VIN, and ascertain whether or not the subject wishes to and/or should continue in the study based on previous noncompliance. In cases where the subject does not return for the rescheduled visit or cannot be reached to reschedule the missed visit, the site should make every effort to regain contact with the subject (3 telephone calls to the subject should be made and if that fails, then a certified letter is sent to the subject's last known mailing address) so that they can be considered withdrawn from the study for disposition purposes. These contact attempts should be documented in the subject's medical record. Should the subject continue to be unreachable, then and only then will she be considered to have withdrawn from the study with a primary reason of "Lost to Follow-up". For all other subjects withdrawing from the study, an alternative reason for discontinuation should be recorded in the eCRF.

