## 6.2 DURING TREATMENT PROCEDURES BY VISIT

Once eligibility has been confirmed, the subject will be randomized to receive study treatment. Visit dates and windows must be calculated from Day 0.

### 6.2.1 DAY 0

The following evaluations will be performed on Day 0 **prior to study treatment**:

- Determination of eligibility per Inclusion/Exclusion Criteria
- Review of concomitant medications and adverse events

- Randomization
- Patient Reported Outcomes
- Targeted physical assessment
- Vital signs
- Urine pregnancy test
- Whole blood and serum for immunologic assay including miRNA profile
- Cervical colposcopy
  - Photographs during colposcopic examinations of the vagina and/or cervical areas should be obtained if lesions are identified.
- Cervical cytology and ThinPrep® for cervical HPV type
  - Collect menstrual cycle status and recent gynecologic history
- OP rinse, vulvar, vaginal and intra-anal swabs
- Vulvoscopy
- Vulvar lesion photography of the qualifying lesion(s)

Study treatment will be administered and the following evaluations will be performed on Day 0 **after study treatment**:

- Post treatment AE and injection site reaction assessment within 30-45 minutes after study treatment
- Distribute Participant Diary (PD)
- Distribute 1 box of imiquimod and the imiquimod dosing log (for subjects in the imiquimod arm)

Download EP data from device within 24 – 48 hours of study treatment

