### **6.2.3 WEEK 4 (± 7 DAYS):**

The following study evaluations will be performed at Week 4 **prior to study treatment**

- Review of concomitant medications and adverse events
- Targeted physical assessment
- Vital signs

- Review imiquimod dosing log and usage (accountability of returned product) for subjects in the imiquimod arm
- Urine pregnancy test
- Vulvar swab
- Vulvoscopy
- Vulvar lesion photography of the qualifying lesion(s)

The following study evaluations will be performed at Week 4 **after study treatment**:

- Post treatment injection site reaction assessment within 30-45 minutes after study treatment
- Patient Reported Outcomes
- Distribute PD
- Distribute 1 box of imiquimod and the imiquimod dosing log (for subjects in the imiquimod arm)

Download EP data from device within 24 – 48 hours of study treatment

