  - viii. Exclusion Criteria #12 has extended the window for use of clinical laboratory results at screening from 30 days to 45 days. This allows subjects to use safety lab results within 45 days prior to Day 0 to determine eligibility
  - ix. Exclusion Criteria #15 has been modified to ensure that subjects do not receive live vaccines within 4 weeks of any of the scheduled doses
  - x. Exclusion Criteria #16 has been modified to ensure that subjects do not receive any non-live vaccines within 2 weeks of any of the scheduled doses
  - xi. Exclusion Criteria previously #22 to #27 now fall under the subgroup of exclusion criteria #18 and are numbered as #18a to #18g. These items include the list of exclusions that fall under the category of current or historically clinically significant, medically unstable disease

- xii. Exclusion Criteria previously #22 (now #18b): Modified to ensure that only subjects with treatment of non-anogenital malignancy within 2 years of screening are excluded from the trial. Subjects in this population could be expected to have anogenital malignancy within 2 years of study start which has been treated and therefore should not be excluded from trial participation
  - xiii. Exclusion Criteria previously #30 to #32 now fall under the subgroup of inclusion criteria 20 and numbered as #20a, #20b, and #20c accordingly. The sub group categorizes subjects with less than two acceptable sites for IM injection
  - xiv. Exclusion Criteria previously #33 to #36 now fall under the category of vulnerable populations and are numbered now #21a, #21b, #21c and #21d
13. The time points for cervical cytology and ThinPrep® have been changed and will be completed at Day 0 instead of at Screening as it is not required for study eligibility. The Week 27 cervical cytology and ThinPrep® has been moved to Week 12 to allow an earlier exploration for prediction of lesion regression from a dosed subject prior to the efficacy timepoint. The cervical cytology and ThinPrep® at Week 74 has been removed and all changes have been updated in the Schedule of Events.
  14. Cervical colposcopy will be completed at Day 0 and Week 96 rather than Screening and Week 96 since cervical colposcopy is not required to determine eligibility on study. This change has been updated in the Schedule of Events.

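### Section 4.3.2 ends biopsies for women who become ineligible, not only where a biopsy is barred, and a vaccine near dose 2, 3 or 4 can be read as triggering it before Week 48

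*Protocol*

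**What the plan says.** **The vaccine criteria.** In the version 2.1 Synopsis, Exclusion 15 is "Received any non-study related non-live vaccine within 2 weeks of each study dose". Exclusion 16 repeats this for live vaccines with a 4-week window. Section 4.2 (version 2.0) has the same text. The version 2.1 Summary of Changes gives the purpose of the non-live criterion: that subjects "do not receive any non-live vaccines within 2 weeks of any of the scheduled doses". The extension to later doses was therefore deliberate. Exclusion 18c, on bleeding disorders and blood thinners, is handled differently: it covers conditions or use "that would contraindicate IM injections within 2 weeks of Day 0".

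**When eligibility is checked.** Table 1 marks inclusion/exclusion criteria at Screening and Day 0 only, and Section 6.2.1 lists "Determination of eligibility per Inclusion/Exclusion Criteria" on Day 0. At Weeks 4, 12 and 24 the relevant line before dosing is "Review of concomitant medications and adverse events".

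**The on-study restriction.** Section 6.16 prohibits the same vaccines, with the same 2- and 4-week windows, around any study treatment. It states no action if the restriction is broken.

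**The consequence.** Section 4.3.2 says: "Subjects who become ineligible to continue on study based on no longer meeting exclusion criteria should be discontinued from study treatment". In full, such subjects are to be "discontinued from study treatment, managed per routine standard of care and should continue on study without further biopsy". The same section opens with a general aim: "All subjects who begin treatment should be encouraged to complete all phases of the study, including those who discontinue treatment".

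**The concern.** The primary endpoint is read from vulvar tissue taken at Week 48, so any rule that cancels a biopsy before then acts directly on the primary analysis. Section 4.3.2 attaches that consequence to ineligibility in general. A restriction that runs to every dose, placed in the exclusion list, gives women a way to become ineligible after entry for a reason that has nothing to do with their lesion.

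A site following that route would lose the Week 48 result of a woman who could perfectly well have been biopsied. If standard care then meant treating her vulvar HSIL, she would be a non-responder by definition. Neither outcome would say anything about whether the study treatment worked.

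**Working it through.** No figure in the plan is in dispute, so the check is a reading of the passages together.

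1. **Can a vaccine after entry meet an exclusion criterion?** By its words, yes. Doses 2, 3 and 4 fall at Weeks 4, 12 and 24, all before Week 48, and Exclusions 15 and 16 reach each of them. A vaccine actually received near those doses cannot be seen at Screening or Day 0.

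2. **What does 4.3.2 mean?** Taken literally the phrase is inverted, because a woman who stops meeting an exclusion criterion becomes eligible. The sentence makes sense only if it means newly meeting one.

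3. **Is the no-biopsy clause limited?** No. Section 7.1.4 uses almost the same formula for carcinoma, where surgical excision makes it appropriate. Section 4.3.2 applies it to ineligibility under the exclusion criteria without qualification. Pregnancy, also an exclusion criterion, has its own rule in 7.1.11, which bars only procedures that are contraindicated. Vaccines have no such rule.

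4. **What happens to the endpoint?** Section 2.1 requires Week 48 tissue. Section 8.4 admits to the mITT set only treated subjects who have the endpoint. Section 8.11.6 allows no imputation. A woman without the biopsy, and without other treatment for her lesion, is therefore absent from the primary analysis. If she receives non-study treatment for vulvar HSIL, Synopsis footnote 4 and Table 3 class her as a non-responder.

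5. **Scale, as context only.** Section 8.3 states 80% power per arm, assuming 90% evaluable: 24 × 0.9 = 21.6 and 12 × 0.9 = 10.8. The exact one-sided test of p ≤ 0.02 at 0.025 rejects at 3 or more responders for n = 21 or 22, and at 2 or more for n = 10 or 11. Power is P(X ≥ r) with X binomial(n, p):

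| Arm | True rate | n | Power | n, one woman fewer | Power |
|---|---|---|---|---|---|
| VGX-3100 alone | 20% | 22 | 84.6% | 21 | 82.1% |
| With imiquimod | 28% | 11 | 85.8% | 10 | 81.7% |

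These values are consistent with the stated 80% as a floor for each arm. They show what one lost biopsy costs if it happens. They do not estimate how often it would, since the documents give no vaccination rate. The planned 10% non-evaluable allowance may already cover a rare loss of this kind.

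**The case against.** The strongest reply is that the protocol never says a vaccine makes a woman ineligible to continue, and that the harm depends on rewording 4.3.2. On this view a vaccine in the window is a breach of 6.16 and is handled as a deviation. Section 9.8 sends deviations to the Sponsor at once. Section 4.3.4 asks for discussion with the Medical Monitor before a violation leads to discontinuation. Section 6 treats adherence to the Schedule of Events as required, and that schedule includes the Week 48 biopsy. Section 4.3.2 itself opens by encouraging everyone treated to complete the study.

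Much of this stands. It makes the lenient reading available and perhaps likely, and medication review before each dose should find some vaccines in time. But none of these passages says that a woman who newly meets an exclusion criterion keeps her Week 48 biopsy. The part of 4.3.2 that preserves all procedures concerns women who choose to stop treatment.

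A reader might also infer that the vaccine criterion does nothing at entry beyond opening the route to 4.3.2. That goes too far. Planned vaccination can be asked about at Screening and Day 0, just as Exclusions 11 and 13d ask about intended pregnancy and anticipated medication. Nor do Exclusions 15 and 16 conflict with 6.16, since the windows are identical.

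**Conclusion.** The point holds as a minor one. The defect lies in 4.3.2: its wording is inverted, and its no-biopsy consequence is not limited to reasons that bar a biopsy. The vaccine criteria are the clearest trigger unrelated to efficacy, but not the root of the problem.

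Two stronger readings are not supported. A reader might infer that the protocol orders the Week 48 biopsy to be dropped after a vaccine. The text permits that reading without stating it, and other passages lean the other way. A reader might also infer a material loss of power. The documents give no rate of affected women, the event is probably infrequent, and no numerical effect is claimed.

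The conclusion rests on three assumptions: that 4.3.2 is meant to cover women who newly meet an exclusion criterion; that a site could regard a vaccine near a later dose as such a case; and that version 2.1 keeps the version 2.0 text of 4.3.2 and 6.16. The version 2.1 change log lists no change to either section, but it also says that unlisted changes are administrative, so a wording correction cannot be excluded.

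**What to change.** In 4.3.2, refer to subjects who newly meet an exclusion criterion. Limit the no-biopsy instruction to carcinoma or other reasons that bar a biopsy, and say that all other women keep the scheduled Week 48 biopsy even if study treatment stops.

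As a consistent tidy-up, tie Exclusions 15 and 16 to Day 0, as 18c does, and let 6.16 govern later doses with a stated action: delay the dose, or record a deviation after discussion with the Medical Monitor. Clearing a 2- or 4-week window may take longer than the ±7 days allowed at Weeks 4, 12 and 24, so 6.16 should say which takes precedence.

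The cost is a few sentences in an amendment. No visit, procedure or analysis is added.

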## STUDY SCHEDULE OF EVENTS

**Table 1: Schedule of Events**

Tests	Screen (-10 wk to -1d)	Day 0	8-14 days post dose 1 Phone Call	Week 4 (± 7 days)	8-14 days post dose 2 Phone Call	Week 12 (± 7 days)	Week 15 (± 7 days)	Week 24 (± 7 days)	Week 27 (± 7 days)	Week 38 (± 7 days) Phone Call	Week 48 (± 7 days)	Week 52 (± 14 days)	Week 74 (± 14 days)	Week 78 (± 14 days)	Week 96 (± 14 days)	Week 100 (± 14 days)
Informed consent	X															
Medical History/Demographics	X															
Medications (prior/concomitant)	X	X	X	X	X	X	X	X	X	X	X	X	X	X	X	X
Socio-behavioral assessment	X										X					X
Inclusion/Exclusion criteria	X	X														
Randomization		X														
Physical exam (PE)/assessment a	X	X		X		X		X	X		X	X	X	X	X	X
Vital signs	X b	X		X		X		X	X		X	X	X	X	X	X
Screening safety (12 lead ECG, labs) c	X															
Pregnancy Testing d	X	X		X		X		X	X		X	X	X	X	X	X
HIV Ab by ELISA	X															
Blood immunologic samples	X e	X e					X e		X f		X e		X e		X e	
HLA testing g									X							
OP rinse, vaginal, and intra-anal swabs		X							X		X		X		X	
Vulvar swabs		X		X		X			X		X		X		X	
Cervical colposcopy		X													X	
Cervical cytology, ThinPrep ® h		X				X					X				X	
Vulvoscopy i	X	X		X		X			X		X		X		X	
Vulvar lesion standardized photography j	X	X		X		X			X		X		X		X	
Biopsy k	X										X		X		X	
Vulvar HPV genotyping l	X										X		X		X	
Inject VGX-3100 +EP lm		X		X		X		X				X m		X m		
Post treatment reaction assessment		X		X		X		X				X		X		
Dispense imiquimod + distribute imiquimod dosing log n		X		X		X										
Review imiquimod dosing log and usage				X		X		X								
Distribute Participant Diary (PD)		X		X		X		X				X		X		
Review PD o			X		X		X		X				X		X	
Adverse Events	X	X	X	X	X	X	X	X	X	X	X	X	X	X	X	X
Patient Reported Outcomes (PROs) p		X	X	X	X	X	X	X	X		X	X	X		X	X

a Full PE mandatory at screening and study discharge (Week 100), otherwise targeted PE as determined by the Investigator or per subject complaints unless signs or symptoms dictate the need for a full PE.

- b Screening vital signs must include a measured height and weight and calculated BMI (Bodyweight in kilograms divided by height in meters squared). Weight will be measured at all dosing visits.
- c Screening 12-lead ECG, complete blood count (CBC), serum electrolytes, blood urea nitrogen (BUN), creatinine (Cr), glucose, ALT, CPK and urinalysis performed within 45 days prior to first dose administration.
- d Negative spot urine pregnancy test is required at screening and prior to each study treatment, vulvoscopy and biopsy/surgical excision.
- e At least 34 mL (4 x 8.5 mL yellow (ACD) tubes) whole blood and 4 mL serum per time point. At least 68 mL whole blood and 8 mL serum should be collected prior to first dose. One additional 8.5 mL yellow (ACD) tube to be collected at Day 0, Week 15 and 48 for microRNA analysis.
- f At least 51 mL [6 x 8.5 mL yellow (ACD) tubes] whole blood and 4 mL serum should be collected at Week 27.
- g HLA testing will be performed once from an existing PBMC sample.
- h HPV genotyping and Pap smears are performed on the same ThinPrep® cervical specimen.
- i An additional visit may be scheduled to perform vulvoscopy if worsening of disease is suspected. Biopsies should not be performed at any visit other than at entry (Screening), Week 48, and Weeks 74 and 96 for Subgroups C and D unless the Investigator suspects invasive cancer. All biopsy samples and/or excision samples must be sent to the PAC for review.
- j Photography of the acetowhite stained qualifying lesion(s) must be performed prior to and after biopsy, and at all vulvoscopy examinations. If a pre-biopsy digital photograph is not available for a historical biopsy sample at screening, a post biopsy photo will be sufficient. Additionally, standardized high resolution digital photographic imaging should be obtained during examinations of the vagina if lesions are identified, for documentation.
- k Tissue specimen from all excised tissue must be reviewed by the PAC and residual vulvar tissue from entry, Week 48, 74 or Week 96 specimen(s) (paraffin blocks or unstained slides) must be sent to the central pathology laboratory for HPV testing.
- l HPV genotyping is performed on vulvar tissue specimen using a PCR based assay.
- m Potential dosing at Week 52 and Week 78 is applicable for partial responders only.
- n Subjects will take home imiquimod plus an imiquimod dosing log to document their use of imiquimod. Administration of imiquimod begins on Day 0.
- o A phone call will be used to review the Participant Diary (PD) with subject within 8-14 days following dose 1 and 2. The patient will be expected to bring the PD to the next visit for review.
- p PRO measures (SF-36v2™, EQ-5D-5L, WOMAN-PRO) plus two additional questions will be assessed as described in [Section 6.8](#).

